### **Risk/Benefit Assessment**

- Risk Category- Low, minimal risk

- Potential Risk - pressure and/or inflammation and/or infection of the nasal cavity, CPAP mask pressure and/or straps holding CPAP mask pressure, mask leaks causing discomfort, tubing restriction of movement and feelings of claustrophobia. Oral appliance discomfort including pressure to the teeth, gums, or jaw joint.
- Protection against Risks - patients will be thoroughly educated on proper CPAP and Oral Appliance use and maintenance. Patients will be given follow-up appointments within one week of initial delivery to troubleshoot and issues and/or side effects. Patients will be told to call or come into the clinic if they have any concerns before their scheduled visit. Scheduled follow-up visits will include attention to side effects or issues to ensure they are addressed. Any side effect and/or issue is expected to be temporary and if intervention is necessary, a full resolution is expected.
- Potential Benefits to the Subjects - The use of the CPAP with the oral appliance has the possibility of assisting subjects with managing their sleep apnea. Successfully managing or improving issues with sleep apnea has been shown to lower high blood pressure, decrease the chance for stroke, reduce blood sugar levels in diabetics, and lower the risk of death. Additionally, results from this study may assist other individuals with sleep apnea in the future.

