## Methods and Procedures

At least fifty patients who were intolerant to CPAP and had a partial response to OAT (AHI greater than or equal to 5 will be recruited randomly and prospectively into one of two groups (at least 25 each in each group). The group options were: 1} Combination therapy with CNMI and 2) Combination therapy with patient's preferred CPAP mask.

These CPAP intolerant patients underwent a PAP titration during an overnight PSG or were assigned an autoPAP and had accumulated at least one month of data. Intolerance to CPAP was defined as patients who reported to their sleep physician that they were intolerant due to CPAP pressure, mask fit/leak issues. They were also asked to fill out a CPAP intolerance questionnaire to document the reason for the intolerance.

Patients who were determined to be partial responders to OAT were determined to have met an adherence and titration protocol. Adherence was defined as using the oral appliance for at least 4 hours per night for 70% of the nights in the 30-day period leading up to the study. The titration protocol includes a minimum of one month of titration along with using patient testimony, bed partner testimony and overnight oximetry to aid in the titration and when tested with an HST or in-lab PSG, the AHI was greater than or equal to 5 (verification sleep test).

Patients who were assigned the option of using their previously preferred CPAP mask, they underwent one CPAP care session and then the two month time period would begin.

If patients were assigned the CNMI option, they were allowed one week for follow up/adjustments of the customized mask, they also underwent one CPAP care session and then the two month time period would begin.

► Data Analysis and Data Monitoring - Data will be analyzed quantitatively using, but not limited to, the Kolmogorov-Smirnov test, Student's *t* test or the Wilcoxon rank- sum test, and SPSS 12.0 for Windows {Chicago, IL, USA}).

Demographic: Ask patients for age and gender

Physiologic: Weight Scale - Weight+ Ruler - Height= Body mass index (BMI)

Pulse Oximeter: Nadir (low O2 saturation), Time percent below 90 {T90}

Polysomnography {PSG}: Apnea-Hypopnea Index (AHI), CPAP pressure, leakage

CPAP Airview or Data Card: AHI, CPAP pressure, leakage

Home Sleep Study (HST): AHI, Nadir, and T90

► Data Monitoring - At time of start of study at [name] Dental Sleep Medicine, PLLC or at J. [name], P.A. Obtain from patient:

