- 1) CPAP intolerance questionnaire
- 2) Compliance questionnaire with oral appliance
- 3) Obtain CPAP data from PAP titration or autoPAP: CPAP pressure, Leakage, Apnea-Hypopnea Index (AHi), Nadir, Time percent below 90 (T90), hours of usage
- 4) Home Sleep Test (HST): AHi, Nadir, T90
- 5) AutoPAP: AHi, mask leakage
- 6) Gather patient demographics: age, gender, BMI

At one (1) Month

- 1) CPAP intolerance questionnaire
- 2) Compliance questionnaire with Oral Appliance
- 3) Gather CPAP data from "Airview" or Data card: CPAP pressure, leakage, AHi,
- 4) Gather oxygen saturation data from Pulse Oximeter: Nadir and T90
- 5) Optional verification (PSG or HST)

After 2nd Month

- 1) CPAP intolerance questionnaire
- 2) Compliance questionnaire with Oral Appliance
- 3) Gather CPAP data from "Airview" or Data card: CPAP pressure, leakage, AHi,
- 4) Gather oxygen saturation data from Pulse Oximeter: Nadir and T90
- 5) Optional verification (PSG or HST)

- Data Storage and Confidentiality- Data will be safeguarded by assigning study participants anonymous identification numbers. Depending on relevant data, it will be stored in a password protected computer with encrypted files in the sleep lab at the Pulmonary & Sleep Center of the Valley to which sub-investigator, [name] may access. At [name], D.D.S., PA and [name] Dental Sleep Medicine, PLLC facilities data will be on a password protected computer with encrypted files to which [name] and research coordinator [name] may access.
- Transition from Research Participation - subjects are patients of record of the clinics.

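### Most of the harms the protocol itself lists have no named data item at month 1 or month 2, and no description of side effects by arm is planned

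*Combined protocol and SAP*

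**What the plan says.** The Risk/Benefit Assessment names the expected harms. On the CPAP side it gives "pressure and/or inflammation and/or infection of the nasal cavity, CPAP mask pressure and/or straps holding CPAP mask pressure, mask leaks causing discomfort", and adds restriction by the tubing and claustrophobia. On the appliance side it gives "Oral appliance discomfort including pressure to the teeth, gums, or jaw joint".

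It then describes how these will be handled. There is an early contact: "Patients will be given follow-up appointments within one week of initial delivery to troubleshoot and issues and/or side effects". For later visits it says "Scheduled follow-up visits will include attention to side effects or issues to ensure they are addressed". It also states that "Any side effect and/or issue is expected to be temporary" and that full resolution is expected if intervention is needed.

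The data to be gathered are itemised separately, under Data Monitoring in Methods and Procedures. Month 1 and month 2 have the same five items:

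- a "CPAP intolerance questionnaire";
- an oral appliance compliance questionnaire;
- CPAP download data (pressure, leakage, AHI);
- oximetry ("Gather oxygen saturation data from Pulse Oximeter: Nadir and T90");
- an optional PSG or HST.

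The outcome list at the end of the Background names AHI, CPAP pressure, mask leakage, Nadir, T90, hours of usage and ESS.

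**The concern.** The section that names the harms and the section that lists the data do not meet. Staff will attend to side effects at visits, but the protocol does not say that the answers become trial data, in what form, or that they will be set out by arm.

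The stated purpose is to compare two combination techniques and to learn whether either or both improve tolerance to CPAP. Side effects are part of tolerance. The arms also differ in a way that could shift them: according to the Background, the CNMI uses the oral appliance as the anchor for the mask, while the other arm keeps mask and appliance separate. Tooth, gum and jaw-joint effects could plausibly differ between arms for that reason, and they are among the harms without a named item. One technique could look favourable on AHI or leakage while causing more of these problems, and the planned data might not show it. The expectation that side effects are temporary could not be checked systematically either.

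**Working it through.** The plan gives no figure on harms to reproduce, so the main check sets its lists side by side.

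**Step 1: listed harms against the month-1 and month-2 items.**

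| Harm in the Risk/Benefit Assessment | Named counterpart at month 1 and month 2 |
|---|---|
| Mask leak discomfort | Yes: device leakage; mask fit/leak is also a named reason for intolerance |
| Mask pressure | Possibly: CPAP pressure is a named reason for intolerance, but that is not the same as pressure from the mask |
| Nasal pressure, inflammation or infection | None named |
| Strap pressure | None named |
| Restriction by tubing | None named |
| Claustrophobia | None named |
| Tooth, gum or jaw-joint pressure | None named |

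The partial coverage comes from the questionnaire, of which Methods and Procedures says: "They were also asked to fill out a CPAP intolerance questionnaire to document the reason for the intolerance". The reasons named there are CPAP pressure and mask fit/leak. The second questionnaire is named for compliance, that is, use.

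**Step 2: other places where harm could appear.** The Background outcome list contains no side effect. The analysis text names the Kolmogorov-Smirnov, Student's t and Wilcoxon rank-sum tests without attaching them to endpoints, and mentions no harm. No section lists a record of stopping CPAP, CNMI or appliance with the reason.

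**Step 3: what recorded data could show.** Group sizes come from the protocol: at least 25 per group, and 50 to 100 in total, so about 50 per group at most if the groups are equal. The event rates below are assumptions, because the documents give none.

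- *No events seen.* The exact two-sided 95% upper limit is 1 − 0.025^(1/n).
  - n = 25: 1 − 0.025^(1/25) = 0.137, or 13.7%.
  - n = 50: 1 − 0.025^(1/50) = 0.071, or 7.1%.
- *Chance of seeing at least one event at an assumed true rate of 5%.* This is 1 − 0.95^n.
  - n = 25: 72%.
  - n = 50: 92%.
- *Power of Fisher's exact test, two-sided alpha 0.05.* This is the sum of the product of the two binomial probabilities over all tables with p ≤ 0.05.

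| Assumed rates | 25 per arm | 50 per arm |
|---|---|---|
| 5% vs 30% | 55% | 90% |
| 10% vs 30% | 30.5% | 64% |

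These sizes support counts with intervals. They do not support a dependable test of harm, least of all at the minimum size.

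**The case against.** The strongest reply is that some of this is already collected. The CPAP intolerance questionnaire is given at the start, month 1 and month 2, and leakage is downloaded at both months. A reader might infer from the gap that the trial will hold no harm data at all; the documents do not support that. Leak, and perhaps part of mask pressure, can be compared by arm. This stands, and the point is confined to the other harms.

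Neither questionnaire is reproduced. The first might ask about straps, claustrophobia or nasal symptoms, and the second might ask why wear was reduced. That cannot be ruled out, so the finding applies to what the plan names. It cannot be assumed either, and no analysis of either questionnaire is stated.

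A reader might also infer that side-effect information will be lost for good. The protocol does not say so. Participants are patients of record of the clinics, and visit notes may hold something. Such notes would probably be unstandardised and incomplete, so they could not be relied on for a comparison by arm.

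Nor does the plan set a rule for declaring one technique the winner. It has no primary endpoint or decision rule, and the purpose allows that either or both techniques may help.

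Finally, the study is rated minimal risk, participants already have CPAP experience and 30 days of adherent appliance use, and both arms combine CPAP with an appliance. No document figure shows that harms differ by arm. This lowers the stakes but does not remove the gap in a comparison that includes tolerance.

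**Conclusion.** The point holds in a limited form. Apart from reasons for CPAP intolerance and mask leakage, the harms the protocol lists (nasal inflammation or infection, strap pressure, tubing restriction, claustrophobia, and tooth, gum or jaw-joint pressure) have no named item at month 1 or month 2. No record of device stops with reasons and no description of side effects by arm is planned. This rests on the lists as printed, and would soften to the extent that the unseen questionnaires cover these harms.

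It would be tempting to add that recording would make a large difference in harm plainly visible. At the minimum size it would not: even the assumed 5% versus 30% has only a little better than an even chance of reaching significance. What would be gained is description by arm, which cannot be rebuilt reliably once the visits have passed. This is a cheap improvement; the trial can run without it.

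**What to change.** Add one item to the month-1 and month-2 lists under Data Monitoring: a checklist of the harms already named in the Risk/Benefit Assessment, each marked yes or no and, if yes, resolved or unresolved. Let the month-1 form cover the time since delivery, so that problems raised at the one-week appointment are included. If the existing questionnaires already ask about some of these harms, say so and add only the rest.

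Record the date and reason for any stop of CPAP, CNMI or oral appliance.

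State in the analysis text that counts and proportions of each harm, unresolved harms and stops will be reported by arm with exact 95% intervals, as description and without a hypothesis test.

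The cost is a one-page form, a few minutes at visits that already address side effects, and one extra table. Treatment, eligibility and sample size are unchanged.

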### **Subject Identification, Recruitment and Consent/Accent**

- Method of Subject Identification and Recruitment - Patients of record of Pulmonary and Sleep Center of the Valley, [name], D.D.S, PA and [name] Dental Sleep Medicine, PLLC who meet inclusion/exclusion criteria will be asked to participate in the study. Research coordinator will read WIRB approved script to recruit patient.
- Process of Consent - [name] and/or [name] will personally read the consent form in the potential subjects' language of choice (i.e. Spanish or English).
  - Give the person providing informed consent as much time as they need to make a decision.
  - If the person providing informed consent needs more time than is allowed by the research design, not enroll the prospective subject.
  - Evaluate whether the person providing informed consent is experiencing time pressure to make a decision, and if so, do not enroll the prospective subject, even if the person providing informed consent agrees to be in the research.
  - Ensure there is no threat of harm or adverse consequences to the prospective subject for a decision to not take part in the research.
  - Stop the informed consent process once the person providing consent indicates that he or she does not want to take part in the research.

- Evaluate whether the person providing informed consent is being coerced or unduly influenced by others to take part in the research, and if so, not enroll the prospective subject, even if the person providing informed consent agrees to be in the research.
- Communicate in the preferred language of the person providing informed consent.
- Adapt the presentation of the information to the subject's capacities in terms of intelligence, rationality, maturity and language.
- Invite and answer questions from the person providing informed consent. Evaluate whether the person providing informed consent understands the information provided, and not enroll a prospective subject who does not understand, even if that person providing informed consent agrees to be in the research.
- Ensure that no information is provided to the prospective subject or the person providing informed consent that is made to waive or appear to waive any of the prospective subject's legal rights, or releases or appears to release the investigator, the sponsor, the institution or its agents from liability for negligence.
- Communicate to the person providing informed consent all the information in the consent document or script approved by the IRB.
- Invite and answer questions from the person providing informed consent

- Consent Forms - WIRB approved consent form.
- Documentation of Consent - [name] will ensure a valid consent is obtained and documented for all participants. Signed consents will be obtained on hard copy (paper) and kept at [name], D.D.S., PA and/or [name] Dental Sleep Medicine, PLLC facilities on a password protected computer with encrypted files to which [name] and [name] may access. A copy of signed consents will be given to each participant.
- Costs to the Subject: Routine costs associated with CPAP therapy. Financial assistance can be granted on a case-by-case basis as normal to daily operations of the clinics.
- Payment for Participation: none
